**Impact of estrogen and progesterone on reward, craving, and response to oxytocin.** Estrogen and progesterone levels fluctuate throughout the menstrual cycle. Progesterone levels peak seven to twelve days after ovulation marking the middle of the luteal phase; estrogen levels dominate throughout the cycle but peak six to ten days after the start of the menstrual cycle, marking the mid-follicular phase (Evans et al., 2002). In addition to sex differences in brain structure, function, and neurochemistry, circulating gonadal hormones play a critical role in mediating the subjective response to the drug itself, cues, and stress. Preclinical studies have localized estrogen and progesterone receptors to brain regions responsible for mediating the physiological and behavioral response to stress and cues (Alves et al., 1998; Cushing & Kramer, 2005; Laflamme et al., 1998). Preclinical studies conducted by MUSC SCOR investigators demonstrated that cocaine seeking is significantly attenuated during the proestrus phase of the estrous cycle when progesterone levels are highest (Feltenstein & See, 2007; Kippin et al., 2005). In a recent study of treatment-seeking cocaine-dependent women, subjective craving following exposure to a laboratory stressor was significantly lower in women with elevated progesterone compared to women with low progesterone (Sinha, et al., 2007). It has also been demonstrated that ovarian hormone levels can impact the response to smoked cocaine with the positive or “rewarding” effects of cocaine significantly lower during the luteal phase compared to the follicular phase (Evans et al., 2002; Sofuoglu et al., 1999). Taken together, these studies indicate that during the follicular phase when estrogen levels are elevated, the positive and rewarding properties of stimulants peak, while increases in progesterone during the luteal phase may decrease craving and/or drug effect.

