
**b. Substance-Related Instruments. Form 90**: The Form 90 (Miller, 1996), an assessment instrument commonly used in substance use studies, is similar in concept to the Time Line Follow-back (Sobell & Sobell, 1992). This is a calendar-based instrument designed to assess daily substance consumption. Study participants will be asked to estimate the amount of substance consumed with the aid of visual cues designed to accurately quantify consumption. Cocaine will be recorded in dollar value, as well as quantity, in order to standardize for different types of cocaine use (crack, IV, nasal, etc.). Alcohol, nicotine, and other drug use will also be tracked. For cocaine use, the data will be summarized in three ways: a) percent of abstinent days (i.e., no use), b) amount of use per day, and c) amount used per using day **Inventory of Drug-Taking Situations (IDTS)** (Annis et al., 1997): This instrument measures typical drug using situations based on Marlatt and Gordon's (1985) eight category taxonomy. This instrument contains eight subscales mapping frequency of use in eight distinct types of situations including use during negative situations (unpleasant emotions) and positive situations (social situations). Although initially calculated to assess alcohol use, this scale has been modified for use with drug abusers and has demonstrated sensitivity to gender differences (Ross et al., 1994). Participants will also be asked to provide a urine sample to be tested for drugs of abuse.

**c. Progesterone and Estrogen Tracking**. We will explore the impact of progesterone and estrogen levels on cocaine craving, stress, and oxytocin effects. Because our hypotheses are related to ovarian hormone levels rather than menstrual cycle phase, direct measurement of hormone levels at the time of testing is the most appropriate measure to address our hypotheses (Becker et al., 2005). As there is significant individual variability in progesterone and estrogen levels across the menstrual cycle, we will measure progesterone and estrogen at the initial assessment and each of the three study visits. We expect that these four samples will provide a profile of hormone levels for each study participant. Since we are interested in having a range of hormone levels for comparison, we will test 50% of participants during the luteal phase when progesterone

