levels are high, and 50% of participants during the follicular phase when progesterone levels are low. Cocaine-dependent women have normal 28-day ovulatory cycles (Evans et al., 2002, Evans & Foltin, 2006; Fox et al., 2008); therefore, we will be able to approximate the menstrual cycle phase by taking a menstrual cycle history during the initial assessment and will schedule the study visits accordingly. Direct ovarian hormone measurement will allow us to utilize all participants' data with absolute progesterone and estrogen levels as continuous measures.

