1. Medication Administration. Participants will be administered 40 IUs of oxytocin nasal spray or matching placebo at 40 minutes prior to study tasks. This dose was selected based on previous studies that have used similar doses of oxytocin (Ditzen et al., 2009; Heinrichs et al., 2003; Kubzansky et al., 2009), as well as our own previous pilot work (see Preliminary Data). Timing of administration is also based on our pilot work and previous studies showing central activity of oxytocin 40 minutes after intranasal administration (Heinrichs et al., 2009). Intranasal oxytocin and matching placebo will be compounded by a MUSC Investigational Drug Service. Randomization will be done by the MUSC Investigational Drug Service, who will keep a record of the blind and be available should unblinding be required. To achieve balance in sample size with respect to gender, a block randomized design with randomly varying block sizes will be used.

2. TSST. The TSST is a standardized psychological stress challenge which has been used extensively in research studies. A meta-analysis supports its utility for evoking a HPA axis stress response in a laboratory setting (Dickerson & Kemeny, 2004). It has induced a robust and reliable physiological stress response in cocaine, marijuana, and alcohol-dependent individuals in our previous studies (McRae et al., 2006; [name] et al., 2011; Waldrop et al., 2010). When the TSST begins, The participant will be told that (s)he will give a speech and perform an arithmetic task. The topic of the speech will be why (s)he should be hired for a particular job (the individual's "dream job"). The participant will deliver the speech as though speaking to a group of potential employers. The experimenter then tells the participant that (s)he has 5 minutes to prepare the speech, and starts the countdown clock (placed in view of the individual). The experimenter leaves the room to allow the participant to prepare. After 5 minutes, three individuals unfamiliar to the participant (the audience) enter the room and are seated; the individual will be instructed by one audience member to stand

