**C.2.d. Statistical Methods.** The hypotheses associated with Aim 1 are interested in the effect of oxytocin on cocaine craving and stress in response to the TSST. It is hypothesized that cocaine-dependent participants receiving oxytocin will demonstrate greater attenuation of stress and craving response to TSST as compared to those receiving matched placebo. A linear mixed effects model containing all serially measured time points will be used to assess the effects of oxytocin versus placebo on each dependent variable. Restricted maximum likelihood (REML; Patterson and Thompson, 1971) methods will be used to estimate the fixed effects and variance components, and baseline values will be used as covariates in the regression models. To test the hypothesis that women will experience greater ameliorative effects of oxytocin on stress and craving response following the TSST as compared to males, similar models will examine the differential (interaction) in the scores reported between men and women by treatment group (oxytocin vs. placebo). Additionally, as an exploratory analysis, the strength of the effects of oxytocin in women will be assessed with differences in estrogen and menstrual cycle phase as independent variables. In a subgroup analysis of women entered into the study, linear mixed effects models will be developed to assess the association of estrogen and menstrual phase (independently) on the stress and craving response to the TSST. Non-linear associations will also be explored using cubic spline models (Marrie et al., 2009). Within each family of dependent measures, the Type I error rate will be controlled using a post-hoc Bonferroni correction.

The hypotheses associated with Aim 2 are concerned with the impact of oxytocin on cocaine cue reactivity. It is hypothesized that oxytocin will decrease cue-induced cocaine craving in cocaine-dependent men and women compared with placebo administration. Post-acquisition preprocessing and statistical analysis will be performed using Matlab 7.8 (Mathworks, Sherborn, MA) with Statistical Parametric Mapping software 8

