##### Exclusion Criteria

1. Women who are pregnant, nursing or of childbearing potential and not practicing an effective means of birth control (not including hormonal contraceptives).
2. Women who are currently taking, or have taken in the past month, oral or other types of hormonal contraceptives or hormone replacement therapies.
3. Women with premenstrual dysphoric disorder who are outside of the follicular phase.
4. Women who have had a complete hysterectomy or are over 50 over one year post-menopausal, as ovarian hormones will be measured in the study.
5. Subjects with evidence of or a history of significant hematological, endocrine, cardiovascular, pulmonary, renal, gastrointestinal, or neurological disease including diabetes, as these conditions may affect physiological/subjective responses. Neurological exclusions include history of stroke, seizure disorders, multiple sclerosis, Parkinson's disease, and Alzheimer's disease.
6. Subjects with Addison's disease, Cushing's disease or other diseases of the adrenal cortex likely to affect hormonal/neuroendocrine status.
7. Subjects with a history of or current psychotic disorder or bipolar affective disorder as these may interfere with subjective measurements.
8. Subjects with current major depressive disorder or post-traumatic stress disorder as these disorders are associated with characteristic changes in stress response.
9. Subjects receiving synthetic glucocorticoid therapy, any exogenous steroid therapy, or treatment with other agents that interfere with hormonal measurements within one month of test session.
10. Subjects taking any mood stabilizers, antipsychotics, benzodiazepines, opiates or opiate antagonists because these may affect test response. Subjects taking SSRI's will be included.
11. Subjects with any acute illness or fever. Individuals who otherwise meet study criteria will be rescheduled for evaluation for participation.
12. Subjects whose height to weight ratio would preclude them from fitting comfortably in the MRI scanner.

13. Subjects who are unwilling or unable to maintain abstinence from alcohol and other drugs of abuse (except nicotine) for three days prior to the stress task procedure.
14. Persons with ferrous metal implants or pacemaker since fMRI will be used.
15. Subjects who are claustrophobic.
16. Subjects with significant psychiatric or medical problems that would impair participation or limit ability to participate in scan.

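### Cycle phase is built into the women's design but is neither balanced nor adjusted for in the Aim 1 models, and PMDD is tied to phase in one exploratory analysis (minor)

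*Combined protocol and SAP*

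**What the plan says.** - **Phase is set by design.** In C.2.c.1.c (Progesterone and Estrogen Tracking) the plan states "we will test 50% of participants during the luteal phase when progesterone" is high, and "50% of participants during the follicular phase when progesterone levels are low". Phase is assigned by scheduling and is not randomised: "we will be able to approximate the menstrual cycle phase by taking a menstrual cycle history during the initial assessment".
- **Phase is expected to matter.** Section A (Significance) concludes that "increases in progesterone during the luteal phase may decrease craving and/or drug effect".
- **Allocation.** C.2.c.2.b.1 (Medication Administration) states: "To achieve balance in sample size with respect to gender, a block randomized design with randomly varying block sizes will be used". Gender is the only balancing factor named. The arm is assigned on Day 1, forty minutes before the TSST, so the scheduled phase is already known.
- **Aim 1 models.** C.2.d (Statistical Methods) says "baseline values will be used as covariates in the regression models". The gender-interaction models are described as similar. Neither contains phase or hormone level.
- **Exploratory women-only models.** The same section plans to "assess the association of estrogen and menstrual phase (independently) on the stress and craving response to the TSST". No PMDD term is mentioned. Hypothesis 1c names estrogen and progesterone, whereas these models name estrogen and phase, so phase stands in for progesterone.
- **Entry rule.** Exclusion item 3 lists "Women with premenstrual dysphoric disorder who are outside of the follicular phase".

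**The concern.** There are two separate issues.

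First, the trial deliberately creates two hormonal groups of women and expects them to differ in craving, yet neither the allocation nor the Aim 1 models take account of them. Luteal and follicular women can fall unevenly between oxytocin and placebo. Any difference in TSST response between phases then enters the women's treatment estimate as noise. That estimate is one half of the comparison with men in Hypothesis 1b.

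Second, on its plain reading exclusion 3 lets a woman with PMDD take part only in the follicular phase. The two phase groups are therefore drawn under different eligibility rules, with every enrolled woman with PMDD on the follicular side. Randomising treatment does not correct this, because phase itself is not randomised.

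**Working it through.** **1. The plan's own figures (C.2.e).** With d = 0.48, 80% power and α = 0.05 (two-sided assumed, since sidedness is not stated), the two-sample calculation gives 69.1 per arm. Rounded up to 70, this is 140 in total. Then 140 × 3.35/4 = 117.25, taken as 118 and rounded to 120. With four gender-by-arm cells, 120/4 = 30 completers per cell. At 80% retention 30/0.8 = 37.5, so 38 per cell and 4 × 38 = 152. The stated figures reproduce. The documents give no figure for phase balance.

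**2. Chance imbalance in phase.** Take 60 female completers, 30 per arm, 30 luteal and 30 follicular, with allocation independent of phase. The luteal count in the oxytocin arm is hypergeometric.
- Variance = 30 × 0.5 × 0.5 × 30/59 = 3.81, so SD = 1.95.
- Arm difference in luteal share = (2x − 30)/30, so SD = 2 × 1.95/30 = 0.130, or 13 points.
- A difference of 20 points or more (18:12 or worse) has probability 0.196. At 19:11 or worse (27 points) the probability is 0.070.
- For all 76 recruited women (38 per arm) the SD is 11.5 points, and the probability of 20 points or more is 0.108.

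**3. Effect on the oxytocin estimate.** Shift in women = difference in luteal share × phase effect. The documents give no phase effect on TSST response, so 0.3–0.5 SD is assumed.
- Typical imbalance (one SD): 0.130 × 0.3 = 0.04 and 0.130 × 0.5 = 0.065 SD.
- At 20 points: 0.06–0.10 SD.
- At 19:11: 0.267 × 0.3 = 0.08 and 0.267 × 0.5 = 0.13 SD.
- Pooled over men and women, with women half the sample, the typical shift is about 0.02–0.03 SD.
- In the gender interaction the women's shift carries through in full, so 0.04–0.065 SD, against the planned differential of 1 SD for craving.

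**4. The same figure against sampling error.** At a single time point the standard error of the women's contrast is √(2/30) = 0.26 SD. A typical shift is 0.04/0.26 = 15% to 0.065/0.26 = 25% of one standard error. Squared, that is about 2% to 6% of the sampling variance. Removing it would shorten the standard error by 1 − √0.98 = 1% to 1 − √0.94 = 3%.

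**5. PMDD and phase.** If a share p of the women have PMDD and all are tested in the follicular phase, they form 2p of the follicular half and none of the luteal half. The documents give neither p nor a PMDD effect. Assuming a 0.5 SD effect, the bias in the luteal–follicular contrast is 0.5 × 2p:

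| Assumed p | Share of follicular half | Bias in phase contrast |
|---|---|---|
| 2% | 4% | 0.02 SD |
| 5% | 10% | 0.05 SD |
| 10% | 20% | 0.10 SD |
| 20% | 40% | 0.20 SD |

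At 5% of 60 women this is 3 people, and at 10% it is 6.

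**The case against.** The strongest reply is that randomisation already deals with the first issue. Allocation is random, so phase imbalance between arms is chance. The oxytocin estimate is unbiased, and its standard error already includes this source of variation. That stands. A reader might infer from the design that the oxytocin effect in women is biased, and the documents do not support this. What is lost is some precision.

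The Aim 1 models also adjust for baseline. Subjective ratings, physiologic measures and cortisol are taken on arrival on the same day, hence in the same phase. Adjustment will absorb part of any phase difference in level and leave mainly differences in reactivity to the task. This stands too, so the shifts above are before that reduction. In the fMRI part each woman receives both treatments, so the issue largely drops out there if both scans fall in the same phase.

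It is also tempting to set the 0.08–0.13 SD shift against the planned stress effect of about 0.49 and call it large. That shift belongs to a 7% event in women only, while the planned effect pools men and women.

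On PMDD, a reader might conclude that Hypothesis 1c is biased by the table's figures. It is not, at least by a PMDD main effect. Hypothesis 1c asks whether the oxytocin effect varies with hormones, and women with PMDD are randomised to both arms, so a main effect cancels in expectation. Only a different oxytocin response in PMDD would disturb that contrast, and the documents offer nothing from which to size one.

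Finally, the plan measures progesterone and estradiol and intends to use them as continuous variables. This mitigates the point but does not remove it, because C.2.d enters hormones in neither the treatment model nor the gender-interaction model, and still uses phase in the exploratory ones.

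**Conclusion.** The point holds as a minor one. Phase is a designed feature, and the plan itself expects it to affect craving, yet it is left out of both the allocation and the Aim 1 models. The cost is noise in the women's TSST estimate and hence in Hypothesis 1b. The typical shift amounts to 15–25% of one standard error, on an assumed phase effect of 0.3–0.5 SD and 30 female completers per arm. The primary conclusion is not threatened.

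The PMDD confounding is structural, and recruiting more women would not reduce it. It is confined to the exploratory women-only association of phase with TSST response, and to the hormone associations as far as hormones track phase. It rests on reading exclusion 3 as applying at testing, and its size cannot be fixed without PMDD enrolment figures.

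**What to change.** - **Aim 1 models that include women:** prespecify either a three-level factor (men, women-luteal, women-follicular) or Day 1 salivary progesterone and estradiol entered within women. Keep treatment-by-gender as the tested interaction. The Day 1 saliva is collected on arrival, before dosing, so no new data are needed.
- **Allocation (optional):** if the list can still be changed, block the women's Day 1 allocation on scheduled phase. With 30 women per arm, one incomplete block then leaves an arm difference in luteal share of at most about 7, 10 or 13 points for blocks of 4, 6 or 8 (2/30, 3/30, 4/30). Block sizes are assumed, and uneven dropout could add to these figures. If the list is fixed, the covariate alone is enough.
- **Exploratory phase and hormone analyses:** prespecify them with women with PMDD omitted or adjusted for, and report how many were enrolled.
- **Reconcile** the half-and-half phase plan in C.2.c.1.c with exclusion item 3, and state at which visit the phase condition applies. No view is taken here on which entry rule is right.

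The sample size does not change. The cost is one or two model terms, a few lines of text and perhaps a few women lost from an exploratory analysis. Phase is known only approximately from menstrual history, and visits move after a positive drug or pregnancy test, which favours measured hormones as the covariate.

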### **C.2.c.2. Session Procedures.**

**a. Session Preparation.** Participants will be informed that they will be expected to remain abstinent from cocaine and other drugs for the three-day period prior to the test sessions in order to minimize the impact of recent drug/alcohol use on stress and cue reactivity. Participants will be asked to come into the office to provide a urine sample once during the three days prior to test sessions to encourage abstinence and session completion. Participants will be instructed to arrive at the Addiction Sciences Division (ASD) on each test day, and to avoid caffeinated beverages on the test day since caffeine can introduce variability to the heart rate response. If the individual is nicotine-dependent, (s)he will be provided with nicotine patches throughout their clinic stay. Upon arriving at the ASD, the participant will be breathalyzed and will provide a urine sample, which will be tested for the presence of amphetamines, d-methamphetamine, cocaine, opioids, THC and benzodiazepines; if female, a urine pregnancy test will also be administered. If the pregnancy and urine drug tests are negative, with the possible exception of THC, the session will proceed. In the event a participant tests positive, the laboratory visit will be rescheduled. A blood pressure cuff will be placed on the subject's arm, and baseline subjective measures, physiologic measures (blood pressure and heart rate), and salivary progesterone, estradiol, and cortisol will be collected.

**b. TSST.** On Day 1, participants will be served lunch and be seated in the ASD testing room where they will be allowed to read or watch television until the TSST testing procedures begin. Forty minutes prior to the TSST, participants will be randomly assigned to receive study medication (intranasal oxytocin or placebo; see Medication Administration). Two more baseline assessments of subjective, hormonal (cortisol), and physiologic measures (blood pressure and heart rate) will be collected, one 20 minutes pre-task and the second 5 minutes pre-task.

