
4. **Discharge.** Following the 60-minute assessment, participants will be given instruction regarding scanning appointments on days 2 and 3. A member of the research staff will be available to discuss management of any craving urges if craving remains elevated at the end of study procedures.

**c. fMRI Sessions.** On Days 2 and 3, participants will be asked to arrive at the ASD. Upon arrival, the participant will be breathalyzed and will provide a urine sample, which will be tested for substances and pregnancy (if applicable). If the pregnancy and urine drug tests are negative, with the possible exception of THC, the session will proceed. In the event that a participant tests positive, the scanning session will be rescheduled. Baseline subjective measures, physiologic measures (blood pressure and heart rate), and

salivary progesterone, estradiol, and cortisol will be collected. Individuals will then be escorted to the Center for Advanced Imaging Research (CAIR; see letter of support) by approved study personnel where MRI scans will be performed.

1. Medication Administration. At the beginning of the session, participants will be screened for metal using a handheld metal detector, and oxytocin (40IU) or placebo will be intranasally administered 40 minutes prior to cue exposure procedures. Although the pharmacokinetics of intranasal oxytocin are not fully understood (MacDonald et al., 2011), given the relatively short half-life of systemically administered oxytocin (approximately six minutes), we would not anticipate carry-over effects from repeated once daily dosing. Further, the order of administration will counterbalanced to obviate order effect; half of the participants will receive oxytocin prior to the first fMRI session and half will receive placebo.

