**C.2.c.3. Follow-Up Procedures.** Participants will return to the research clinic once weekly for the two weeks following completion of scanning procedures. At each visit, a urine drug screen will be obtained and TLFB data on cocaine and other drug use will be obtained. Participants will have had a brief period of monitored abstinence during testing procedures (3 days prior to testing, 3 days during testing); measurement of relapse to cocaine use after early abstinence in a clinical population provides homology and integration with Project III, which is assessing similar outcomes in a preclinical model. At each follow-up visit, measures of daily stress will be obtained using the 10-item Perceived Stress Scale (PSS; Cohen et al., 1983), and subjects will be asked to

specifically assess possible precipitants of use when cocaine use is reported. The PSS has been used previously in cocaine dependent adults (Fox et al., 2009; Hyman et al., 2007), and has demonstrated test-retest reliability. The menstrual history diary will be updated at each visit. Following study completion, referrals to treatment programs will be provided to all participants. At the first follow-up visit, blood will be collected from consenting participants for genetic testing.

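### The six-minute half-life does not rule out carry-over between scan days, counterbalancing does not remove it, and the joint allocation of Day 1 arm and scan order is unstated

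*Combined protocol and SAP*

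**What the plan says.** Study drug is given on three test days. On Day 1 (C.2.c.2.b, TSST), "Forty minutes prior to the TSST, participants will be randomly assigned to receive study medication". On Days 2 and 3 (C.2.c.2.c, fMRI Sessions) each participant has one scan on oxytocin and one on placebo: "half of the participants will receive oxytocin prior to the first fMRI session and half will receive placebo". C.2.c.3 (Follow-Up Procedures) describes the abstinence period as "3 days prior to testing, 3 days during testing", so doses are about a day apart unless a positive test leads to rescheduling.

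Carry-over is dismissed in the fMRI Medication Administration paragraph: "given the relatively short half-life of systemically administered oxytocin (approximately six minutes), we would not anticipate carry-over effects from repeated once daily dosing". That sentence opens with a caveat, "Although the pharmacokinetics of intranasal oxytocin are not fully understood". The next one says that "the order of administration will counterbalanced to obviate order effect". In the TSST Medication Administration paragraph, the dosing time rests on pilot work and on "previous studies showing central activity of oxytocin 40 minutes after intranasal administration".

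The only stated restriction on randomisation is blocking for balance by gender. C.2.d (Statistical Methods) gives Aim 2 no period, sequence, Day 1 or previous-dose term. It compares drug conditions with independent-samples t-tests at the second level, and makes treatment a between-subjects factor in the connectivity ANOVAs.

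**The concern.** A half-life for systemic drug describes clearance from the circulation. The plan expects a central effect when, on that half-life, almost no systemic drug is left, so the figure cannot say how long the effect lasts. It is also silent on behavioural carry-over, such as having viewed the cocaine cues under drug the day before.

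Counterbalancing is then asked to do something it cannot. With half the participants in each order, a period effect averages out of the drug contrast, but carry-over from the first scan's dose to the second scan does not. Carry-over in the same direction as the drug effect would pull the Aim 2 contrast towards zero, and no check for it is planned. A further dose, randomised on Day 1, precedes the scans, and its relation to scan order is not described.

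**Working it through.** **Inputs from the documents.** Half-life about 6 minutes and scan order 1:1 (fMRI Medication Administration). Central activity at 40 minutes (TSST Medication Administration). TSST of 15 minutes, measured to 60 minutes afterwards. 120 completers (C.2.e). The documents give no carry-over value and no stated Aim 2 figure to reproduce.

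**Step 1: what the half-life implies.** Fraction remaining = 0.5^(t/6).
- t = 40 min: 40/6 = 6.7 half-lives, 0.98% remaining.
- t = 40 + 15 + 60 = 115 min (last TSST assessment): 19.2 half-lives, 0.0002% remaining.
- t = 24 h = 1,440 min: 240 half-lives, effectively nothing.

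The plan measures effects where the half-life predicts almost no drug, so the half-life does not govern the effect. This does not show persistence to the next day. For 1% to remain at 24 h the effective half-life would have to be 24 x ln 2/ln 100 = 3.6 h; for 10%, 24 x ln 2/ln 10 = 7.2 h. Both are assumed scenarios.

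**Step 2: bias from carry-over.** Let tau be the drug effect, pi the Day 3 minus Day 2 period effect, and lambda the carry-over from the previous dose. Write sequences as Day 1 | Day 2 Day 3. The oxytocin-minus-placebo scan difference d has expectation:

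| Sequence | E(d) |
|---|---|
| O\|OP | tau - pi |
| O\|PO | tau + pi - lambda |
| P\|OP | tau - pi - lambda |
| P\|PO | tau + pi |

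With equal numbers the mean is tau - 2 lambda/4 = tau - lambda/2. Take only the two placebo-on-Day-1 rows and the mean is again tau - lambda/2, so the bias comes from the Day 2 dose.

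In general, with half in each scan order, bias = -lambda/2 + (lambda/2) x [P(Day 1 oxytocin | oxytocin first) - P(Day 1 oxytocin | placebo first)].
- Day 1 arm independent of scan order: the bracket is 0 and the bias is -lambda/2. Chance imbalance with 60 per order adds an SD of 0.5 x sqrt(2 x 0.25/60) = 0.046 lambda.
- Day 1 dose always the same as Day 2: bias 0.
- Day 1 dose always the opposite of Day 2: bias -lambda.

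Simulation (4,000 runs, 120 completers, true effect -0.50, lambda -0.25, both assumed) gave -0.376, -0.501 and -0.248, against -0.375, -0.500 and -0.250 from the formula.

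**Step 3: cost of adjusting, four sequences of 30.** Least squares on the differences has columns tau (1,1,1,1), pi (-1,1,-1,1) and lambda (0,-1,-1,0). In units of var(d)/120 the variances are tau 2 and lambda 4; without lambda, tau is 1. The standard error (SE) of tau rises by sqrt(2) = 1.41. Generalised least squares, which recovers between-person information, gives the following for an assumed correlation rho between the two scans. The value 0.78 is borrowed from the Aim 1 outcomes.

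| rho | SE tau, unadjusted to adjusted (SD) | Ratio | Carry-over detectable at 80% power (SD) |
|---|---|---|---|
| 0.3 | 0.108 to 0.131 | 1.22 | 0.42 |
| 0.5 | 0.091 to 0.115 | 1.26 | 0.40 |
| 0.78 | 0.061 to 0.081 | 1.34 | 0.30 |

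A plain comparison of Day 1 arms at the Day 2 scan (60 v 60) detects about 0.52 SD.

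**Step 4: does one lambda suffice?** Let L1 be Day 1-to-2 and L2 be Day 2-to-3 carry-over. In table order the expectations become tau - pi + L1 - L2, tau + pi - L1, tau - pi - L2 and tau + pi. Raising tau by 1, lowering pi by 1 and raising L2 by 2 leaves all four unchanged, so the system has rank 3 for four unknowns. L1 can be estimated within person and L2 cannot, yet the bias under balance is -L2/2.

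**The case against.** The strongest reply is that nothing in the documents points to a next-day effect. Six minutes refers to systemic drug and 40 minutes to central activity after intranasal dosing. A reader might infer that one figure contradicts the other, or that together they demonstrate carry-over. They do neither: they measure different things, the plan concedes its uncertainty about intranasal pharmacokinetics, and an effect at 40 minutes says nothing about 24 hours. This part of the reply stands.

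A reader might also infer that the Day 1 dose biases the Aim 2 contrast. The documents do not support that. They are silent on how Day 1 arm and scan order combine, and silence is not imbalance. If the two are independent, the Day 1 dose adds only chance noise. The once-daily wording in the rationale may itself cover Day 1; the omission is in the analysis.

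Nor is the previous-dose model a full check. Step 4 shows that it needs L1 = L2, which is doubtful because Day 1 is a social stressor and Day 2 a cue task. It is also weak. If, purely as an assumption, the true effect were 0.5 SD and 20-50% of it persisted, carry-over would be 0.10-0.25 SD, below the detectable 0.30-0.42 SD. The contrast would still keep 75-90% of the effect, so it would go too far to say that a null Aim 2 result could not be told from contamination.

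What the reply leaves standing is that the stated reason for excluding carry-over is uninformative, that counterbalancing is credited with too much, and that the allocation and the model leave the matter unaddressed.

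**Conclusion.** The point holds in a limited form. The half-life does not establish how long a central or behavioural effect lasts, and counterbalancing does not remove carry-over. If a first-order carry-over lambda exists, the Aim 2 contrast is biased by -lambda/2, arising from the Day 2 dose. An assumed 20-50% persistence would understate the effect by 10-25%. No value of lambda can be taken from the documents, and it may be zero.

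The size assumes that both scans of every completer are used, equal numbers in each order, and Day 1 arm independent of scan order. Only an association between the last two would move the bias, at the extremes to 0 or -lambda, and the plan should exclude that by stating the joint allocation. If Day 1 dose were always opposite to Day 2 dose, drug effect and carry-over could not be separated within person.

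**What to change.** 1. **Allocation.** For participants not yet allocated, have the Investigational Drug Service assign scan order in blocks within Day 1 arm and sex. Report the realised counts in the four sequences.
2. **Main Aim 2 analysis.** Use a within-person oxytocin-placebo model with scan period and Day 1 arm, replacing the between-subjects handling of drug in C.2.d. The precision figures above refer to this type of model, not to the analysis now written.
3. **Sensitivity analysis.** Prespecify a model with a previous-dose term, recording the actual interval because sessions can be rescheduled, and state the L1 = L2 assumption. Also compare the pre-dose subjective, physiologic and cortisol measures on Days 2 and 3 by previous dose. These are already collected, and the Day 3 comparison bears directly on the Day 2 dose, though not on the scan outcomes themselves.
4. **Wording.** Say that the systemic half-life does not settle the duration of effect, and that counterbalancing balances period effects only.

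The cost is a revised allocation list and a rewritten Aim 2 analysis paragraph. Dosing, visits and sample size do not change. The adjusted drug effect has a standard error about 1.2 to 1.4 times larger, the check detects only carry-over of about 0.3-0.4 SD, and the Day 2-to-3 term is not identifiable within person if the two carry-overs differ. The adjusted analysis should therefore stay secondary. If enrolment is too advanced to rebalance, items 2 to 4 and the report of realised counts remain possible.
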